2. To run a feasibility RCT to evaluate recruitment and retention rates for a future efficacy RCT, for example recruitment rates for schools and participants, attrition rates and outcome measure completion.
3. To assess the acceptability of the intervention to participants using post-therapy feedback questionnaires.

Secondary aims:

1. To gather descriptive data on symptom-change to inform sample size estimates for a future fully powered RCT of clinical and cost-effectiveness.
2. The secondary aim is to collect pilot data on clinical measures as well as on the underlying mechanisms proposed to be targeted in the intervention. This will include measures of imagery vividness, emotional response to positive future imagery and memory specificity.

Methods/ designs

Study design and timeline

In the case series all participants will receive the intervention. Participants will be recruited from multiple school/ college sites in the United Kingdom. Participants will be assessed at pre-intervention (prior to randomisation) and at follow-up, after the intervention, and at a 3-month follow-up after the intervention. For the feasibility randomised controlled trial, participants will be randomly allocated to either the intervention group or a control group (non-directive supportive therapy). Both of these are active interventions that aim to improve mood and self-esteem. Participants will also be recruited from multiple school/ college sites in the United Kingdom. Participants will be assessed at pre-intervention (prior to randomisation) and at follow-up, after the intervention, and at a 3-month follow-up after the intervention.

Study population

Inclusion criteria

1. Aged 14-19
2. Informed consent
3. Willing and able to engage in psychological therapy and complete assessments
4. Scoring above clinical cut-off on the MFQ (29 items; clinical cut-off ≥ 17), and showing high symptoms of anhedonia, as measured by the SHAPS (14 items; abnormal level of hedonic tone > 2)

Exclusion criteria

1. Diagnosis of learning disability (but not difficulty e.g. dyslexia), diagnosis of Autism Spectrum Disorder, or significant head injury, neurological disorder or epilepsy
2. Unable to fluently communicate in spoken English

3. Unable to give informed consent
4. High levels of current risk
5. Currently receiving therapy (including school counselling)

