6. Experiencing psychotic symptoms or depressed in the postnatal period (participants with co-morbid physical illness or non-psychotic disorders such as anxiety will not be excluded)

Setting

The intervention will be delivered face-to-face. The practitioner delivering the intervention will be working from a private workspace and participants will receive the intervention at school in a private designated space. Participants will complete their screen and assessment questionnaires online using Qualtrics.

Sample size

For the case series, 10 participants will be recruited. As the purpose of the trial is to assess feasibility and not efficacy, a power calculation to determine sample size is not appropriate. The data from this trial could however be used to inform a sample size calculation for a future efficacy trial. The target sample size (n=32; 16 in each arm) was determined with reference to good practice recommendations for feasibility/ pilot studies, which recommend sample sizes of between 24 and 50 (Julious, 2005; Lancaster, Dodd, & Williamson, 2004; Sim & Lewis, 2012). The sample size of 50 was inflated to allow for drop-out following randomisation, which was estimated to be 10% based on similar studies (Smith et al., 2015).

Recruitment (case series and trial), randomisation and blinding (trial only)

All participants will be recruited from a secondary school or sixth form college. The project researcher will liaise with the school gatekeeper and present the study to all students aged 16 to 18. All students will be provided with an information sheet at least 24 hours before the presentation to consider taking part. Following the presentation, all students will be invited to complete the screen questionnaire online if they wish to do so. At the screening stage we will ask the students' consent to inform the pastoral lead/ gatekeeper of their interest in the study, to ensure there is a private space at school for them to complete their sessions. Following the screen, eligible participants will be identified by scoring above clinical cut-off on the Mood and Feelings Questionnaire (MFQ) and showing high symptoms of anhedonia on the Snaith Hamilton Pleasure Scale (SHAPS). At the first assessment, the MFQ and SHAPS will be administered again, and participants will be assessed against the eligibility criteria. As participants will be over the age of 16, we will not seek parental

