- Recruitment and retention rates: will be described as percentages and predicted vs. actual recruitment rates will be recorded monthly
- Trial flow CONSORT diagram: will be used to show the number of approached participants, numbers eligible/ ineligible

Service user involvement

Service user advisory groups were consulted during the development of the intervention and their feedback was positive, identifying a unmet need for young people with depression and a treatment strategy that was novel to them.

Data management and dissemination

Participant data will be anonymised, and participants will be given a unique code. Consent forms will be stored separately. All anonymised data will be stored on a password-protected computer and backed up on an encrypted USB. We intend to disseminate the findings to the schools that participated in the research, as well as more widely through conferences and publications in peer-reviewed scientist journals. Following completion of the trial, the data set will be made publicly available.

Ethical issues and ethical approval

KCL ethics has granted ethical approval for the project (KCL Ethics Ref: HR-19/20-14899) to be delivered in school-settings. Ethical issues include ensuring informed consent is gained, disclosure of risk issues, confidentiality and potential to cause distress and stigma.

Informed consent: this will be sought at both the screening and intervention stages. The project will first be explained verbally to participants and they will be informed that participation is voluntary. At each stage participants will receive an information sheet which explains that they will be asked for informed consent before participation. Informed consent will be completed on Qualtrics, where participants will tick their agreement and provide their name and date of consent. This informed consent will be initially saved on Qualtrics. Should participants wish to have a copy of their consent form, it can be downloaded and saved as an encrypted file which can then be shared with the participant

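### The drop-out sentence inflates a sample size of 50, which does not fit the stated RCT target of 32 (16 per arm), and the basis of the 10% allowance within 32 is not given

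*Combined protocol and SAP*

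**What the plan says.** All the relevant text is in the Sample size section, under Methods/designs.

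- No formal calculation is made; the section says that "a power calculation to determine sample size is not appropriate".
- One RCT target is labelled as such: "The target sample size (n=32; 16 in each arm) was determined with reference to good practice recommendations for feasibility/ pilot studies". Those recommendations are summarised as ones "which recommend sample sizes of between 24 and 50".
- The following sentence deals with attrition: "The sample size of 50 was inflated to allow for drop-out following randomisation, which was estimated to be 10% based on similar studies".
- The case series is separate, with 10 participants.

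No other section gives the RCT a size of 50, a total after inflation, or an expected number of completers.

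Two other places bear on why the number matters. The second primary aim is "To run a feasibility RCT to evaluate recruitment and retention rates for a future efficacy RCT". Statistics and data analysis then says: "Recruitment and retention rates: will be described as percentages and predicted vs. actual recruitment rates will be recorded monthly".

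**The concern.** Two consecutive sentences give different sample sizes for the same trial. The sentence naming 50 is also the only text about the drop-out allowance. Once it is seen not to fit 32, nothing explains how the 10% entered the target or how many participants are expected to remain.

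Little is at stake for inference, because the listed analyses are descriptive. The cost is to clarity in a trial whose purpose is to measure recruitment and retention: it should have one unambiguous number to randomise and one expected number retained. A site, funder or later author who takes the drop-out sentence at face value could report the wrong planned size.

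**Working it through.** **Inputs, all from the Sample size section:** target N = 32, or 16 per arm; cited range 24 to 50; size named in the drop-out sentence, 50; drop-out d = 0.10; case series, 10.

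**Formulae.** The usual inflation is N/(1 − d). The common shortcut is N × (1 + d). Both were tried, rounding up to whole participants. Expected retained = N × (1 − d).

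**Step 1. Can 32 be reproduced from a stated figure?**
- From 50: 50/0.9 = 55.6, so 56; or 50 × 1.1 = 55. Neither is 32, and both exceed the top of the cited range.
- From 24, the lower end of the range: 24/0.9 = 26.7, so 27; or 24 × 1.1 = 26.4, so 27. Neither is 32.
- Adding the case series to the target: 32 + 10 = 42, which is not 50.

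**Step 2. What would link 50 and 32 directly?**
- From 50 down to 32: 1 − 32/50 = 36% drop-out, not 10%.
- From 32 up to 50: 50/32 − 1 = 56% inflation, not 10%.
- If 50 were the total after inflation, the base would be 50 × 0.9 = 45, a number not in the plan.

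**Step 3. Which bases do give 32?**
- 28/0.9 = 31.1, rounded up to 32 for equal arms. Per arm, 14/0.9 = 15.6, so 16.
- 29 × 1.1 = 31.9, so 32.

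Neither 28 nor 29 is stated. So 32 is arithmetically compatible with a 10% allowance already applied, but the plan does not show it.

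**Step 4. Is 32 randomised consistent with the plan's own rationale?**
- Expected retained: 32 × 0.9 = 28.8, about 29, which lies inside 24 to 50.
- Probability that at least 24 of 32 are retained at 90% retention, binomial with independent drop-out: 0.997.

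**Step 5. Does the ambiguity affect precision?** For comparison only, suppose 32 were the size before the allowance: 32/0.9 = 35.6, so 36 randomised and 36 × 0.9 = 32.4 retained.
- Exact 95% confidence interval for retention: 75% to 98% for 29/32, against 74% to 97% for 32/36.
- 95% limits for a pooled SD as multiples of the estimate (degrees of freedom N − 2): 0.791 to 1.361 with 29 retained, against 0.799 to 1.337 with 32 retained.

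These are practically the same.

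**The case against.** The strongest reply is that this is a slip and that 32 is plainly the target. It is the only figure labelled as such, and it is split into 16 per arm, which reads as the number allocated. Drop-out is defined as happening after randomisation, so it comes out of that number. The inflation is described in the past tense, so it has already been applied. Bases of 28 or 29 make this arithmetically possible. All of this stands, and it is why 32 randomised with the allowance included is the natural reading. It does not rescue the sentence, which attaches the inflation to 50. Reading 50 as the top of the recommended range does not help either, since inflating it gives 55 or 56.

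It is also fair to say that no calculation is shown and then miscomputed. This is an internal inconsistency in a stated figure, and a feasibility trial needs no power calculation. Both points are accepted.

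Three stronger inferences are tempting, and the documents do not support them.

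- That the trial was really meant to randomise 50 or 56. This sets aside the explicit target and arm sizes, and no other text gives either total for the RCT.
- That 32 is the size before the allowance, so that 36 (18 per arm) are needed and recruiting 32 would be only 32/36 = 89% of target. The figure 36 appears nowhere, and this reading treats an inflation described as done as still to come.
- That recruitment and retention will be judged against this total and the 10%. Statistics and data analysis promises percentages and a monthly record of predicted and actual recruitment rates. It does not derive the prediction from the sample size, make 10% a benchmark, or set a threshold on either.

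**Conclusion.** The sentence naming 50 is wrong as written: no stated input reconciles 50, 10% and 32. The basis of the drop-out allowance within 32 is also unstated, although the wording favours 32 randomised with the allowance included and about 29 retained.

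This is a minor point. On the natural reading the number to recruit does not change at all. There is no power calculation to disturb, and the observed recruitment and retention rates keep valid denominators whatever the intended total. Even against a total of 36, the width of the intervals barely moves.

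The conclusion that the figures conflict rests only on the plan's own numbers. The expected 29 retained assumes the plan's 10% drop-out, and the 0.997 probability also assumes that participants drop out independently. Any claim that the results will be compared with this total or with 10% would be a further assumption.

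**What to change.** Replace the sentence about 50 with one that gives a single number to randomise and a single number expected to be retained. For example: *Target n=32 randomised (16 per arm); at an estimated 10% drop-out about 29 are expected to be retained, within the recommended 24-50.* Then use 32 consistently as the recruitment target.

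The cost is one sentence of protocol wording. The only downside is that the plan openly states about 29 retained. No extra enrolment is proposed.

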Whilst these studies suggest promising treatments for upregulating positive affect in adults, to our knowledge, there are no such treatments available for adolescents with anhedonia. This is problematic because in the UK, 50-78% of young people with MDD report experiencing anhedonia (Orchard, Pass, Marshall & Reynolds, 2016; Goodyer et al., 2017). Furthermore, in adolescents, anhedonia is a greater predictor of poor treatment outcomes than other symptoms of depression and may be a key factor in adolescent suicidality. Despite promising initial findings from these treatments in adults, it cannot be assumed that identical effects will be found in adolescents because this is a time of rapid emotional and cognitive development, including the strengthening of 'top-down' cognitive control, goal-directed behaviour, working memory and attention allocation (Yilmaz et al., 2019; Beatriz et al., 2013). For example, whilst the use of dampening appraisal appears to be a maintenance factor of anhedonia in adolescents, the effects are said to be smaller than in adults (Yilmaz et al., 2019). Furthermore, these interventions, like much of traditional cognitive therapy, use verbal processing approaches. However, imagery-techniques may be more developmentally appropriate for adolescents (Pile et al., 2018). There is increasing evidence that mental imagery may target currently neglected but potentially beneficial cognitive processes in treating depression. For example, harnessing positive imagery rather than verbal thoughts, may have a greater impact on positive affect (Boland et al., 2018; Holmes et al., 2016). Lastly, these interventions targeting anhedonia in adults are lengthy (>8 sessions), making them more expensive and less accessible.

Mental images are characterised as 'seeing with the mind's eye' and unlike verbal thoughts are considered to have close access to sensory information (Kosslyn, Ganis & Thompson, 2001). Mental images can be positive or negative and vary from being deliberately brought to mind (i.e. planning

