- Time needed to collect (through online methods) and analyse data
- Data completeness and reasons for missing data
- Unexpected adverse effects
- Follow-up rates, adherence/ compliance rates and response rates to questionnaires at each time point (recruitment, intervention and follow-up).

Acceptability data

Participants will be asked to complete a feedback questionnaire about their experiences of the intervention itself and of it being delivered in school.

Secondary

Clinical outcome measures will be collected at baseline (pre), post and 3-month follow-up. These include measures of depression and anhedonia to measure the proposed mechanisms of therapeutic change.

- Mood and Feelings Questionnaire (MFQ) (Angold et al., 1995) is a 33-item measure of low mood in young people rated on a 3-point Likert scale. We have removed the risk items so will administer a 29-item version.
- Snaith-Hamilton Pleasure Scale (SHAPS) (Snaith et al., 1995) is a measure of anhedonia, consisting of 14 items rated on a 4-point Likert scale.
- Positive and Negative Affect Schedule (PANAS) (Watson, Clark & Tellegen, 1988) is a self-report measure of affect and consists of 20-items rated on a 5-point Likert scale.
- The Prospective Imagery Task (PIT) (Holmes et al., 2008; Stober, 2000) adapted for use in young people by (Pile et al., 2018). Fourteen scenarios (7 positive and 7 negative) are presented to participants (e.g. "You will achieve something you wanted to"), who are asked to imagine each happening to them and then rate this mental image on a 5-point scale; 'No image at all' to 'Very clear and detailed'.
- Autobiographical Memory Task (AMT) (Williams & Broadbent, 1986) is a measure of memory specificity. Participants will be given an example of a specific memory and then asked to give a specific memory to ten cue words (five positive; five negative).
- Screen for Child Anxiety Related Disorders (SCARED, Birmaher et al., 1997) is a self-report measure of anxiety, consisting of 41 items rated on a 3-point Likert scale.
- Rosenberg Self Esteem Scale (RSES) (Rosenberg, 1965) is a 10-item self-report measure of self-worth, rated on a 4-point Likert scale.

Statistics and data analysis

All analyses will be conducted on an intent-to-treat basis:

- Descriptive statistics: including means and standard deviations for normally and not normally distributed data will be reported for key outcomes from the feasibility RCT data

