Disclosure of risk issues: Prior to participating, the young person will be informed that everything they say is confidential unless the project researcher is concerned that they may be at risk to themselves or others. If participants make a disclosure, the project researcher will seek support from the clinical supervisor (VP) in supervision or during the session with the young person if immediate risk is indicated. The project researcher will then contact the pastoral lead/ gatekeeper at school, who will follow their school safeguarding procedures on managing the risk, including disclosure of risk to parents or local authorities (including social services and the police if illegal activities are indicated). All participants will be given a leaflet about mental health and where to access help. Depending on the nature of the disclosure, advice about help for young people will be given, including referral to local CAMHS services.

Potential to cause distress: it is possible that participants may experience distress during the therapy when describing feelings of low mood. Prior to the intervention, participants will be informed they can contact me in confidence to discuss any issues. Should any concerns need to be managed I will utilise my on-going supervision and if necessary, contact gatekeepers at participating schools.

Stigmatisation: this is an important issue and we have taken a variety of measures to ensure participants associated with the project will not be stigmatised. As screening and assessments will be online, young people will not see each other's responses. Young people who meet the eligibility criteria will be invited to the intervention stage via email or text message and if they wish to take part, they will need to contact me. This is to ensure their participation is voluntary and not identifiable to other students. Furthermore, whilst participants need to score above clinical cut-off to be eligible for the study, we state on our participant information sheet that "depending on responses to the questionnaires, we will ask pupils with a range of mood scores to take part in Stage 2". If participants do experience stigmatisation, we will liaise closely with the school and their policies on bullying to ensure the best course of action is taken. Participants may also discuss the issue of stigmatisation with me and are free to withdraw from the study at any time.

References

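### The only harm outcome is limited to undefined 'unexpected' adverse effects, so the distress, risk disclosures and stigmatisation that the protocol foresees would not be counted as harms

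*Combined protocol and SAP*

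**What the plan says.** All references are to the combined protocol and SAP.

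- **Outcome measures, Primary, Feasibility data.** The sole harm item is "Unexpected adverse effects". The document does not define an adverse effect, say what makes one unexpected, or state who records it, when, or by arm.
- **Statistics and data analysis.** The plan covers descriptive statistics for key outcomes, recruitment and retention percentages, and a CONSORT diagram. It has no summary of harms.
- **Ethical issues and ethical approval.** The opening paragraph states: "Ethical issues include ensuring informed consent is gained, disclosure of risk issues, confidentiality and potential to cause distress and stigma". On distress it says "it is possible that participants may experience distress during the therapy when describing feelings of low mood". On risk it says "If participants make a disclosure, the project researcher will seek support from the clinical supervisor". On stigma it says "If participants do experience stigmatisation, we will liaise closely with the school and their policies on bullying". Each is followed by a way of handling the event. None is followed by a rule for recording or reporting it as an outcome.
- **Outcome measures, Secondary.** On the MFQ: "We have removed the risk items so will administer a 29-item version". No other listed questionnaire is described as measuring self-harm or suicidality.
- **Background.** Anhedonia in adolescents "may be a key factor in adolescent suicidality".

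**The concern.** An event that the protocol has foreseen, and for which it has written a procedure, is not unexpected in the usual sense of the word. Read that way, the harm outcome leaves out the very events that the authors thought most likely. The questionnaires do not fill the gap for risk, because the MFQ risk items have been taken out and nothing listed replaces them.

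The randomised trial is meant to inform the decision whether a full-scale efficacy trial is warranted. That decision, in depressed adolescents, needs a count of harms in each arm. As the plan stands, the trial could truthfully report no adverse effects under its own outcome while several participants had become distressed to the point of needing action, disclosed risk, or been stigmatised for taking part.

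**Working it through.** The plan gives no figure on harms, so there is none to reproduce. The check is a comparison of the text, followed by an illustration.

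**1. Foreseen events against the outcome list**

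| Event foreseen in the ethics section | Handling stated | Counted as a harm outcome |
|---|---|---|
| Distress during therapy | Supervision; school gatekeeper if necessary | No |
| Disclosure of risk | Clinical supervisor, then school safeguarding | No |
| Stigmatisation | School and its bullying policies | No |

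**2. Other places where harm might surface**

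- Reasons for drop-out (primary feasibility data) show a harm only if it ends participation.
- Reasons for missing data show a harm only if it leads to missing responses.
- The feedback questionnaire covers experience of the intervention, but no harm content is stated.
- MFQ, SCARED and PANAS scores at baseline, post and 3 months can show worsening symptoms. The MFQ used has 33 − 29 = 4 fewer items than the full version, and the items removed are the risk items.
- The recruitment and blinding section says Good Clinical Practice will be followed. No definition, collection procedure or report of adverse events is attached to that sentence.

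These are partial sources. None is set up as a harm outcome.

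**3. Would there be events to count?**

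The documents give no event rates, so the rates below are assumptions. Inputs: n = 16 per arm and 32 in total (Sample size section). The chance of at least one participant with an event is 1 − (1 − p)^n.

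| Assumed true rate p | One arm, n = 16 | Both arms, n = 32 |
|---|---|---|
| 5% | 1 − 0.95^16 = 56% | 1 − 0.95^32 = 81% |
| 10% | 1 − 0.90^16 = 81% | 1 − 0.90^32 = 97% |
| 20% | 1 − 0.80^16 = 97% | 1 − 0.80^32 = above 99% |

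Across this range, at least one event in the trial is likely.

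**4. What a report of zero would mean**

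The exact two-sided 95% upper limit for zero events in n is 1 − 0.025^(1/n).

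- n = 16: 1 − 0.025^(1/16) = 20.6%
- n = 32: 1 − 0.025^(1/32) = 10.9%

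These limits follow from the sample size alone. They can be read as limits on the harm rate only if every relevant event has been recorded. They do not measure what is lost by leaving foreseen events out.

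**The case against.** The strongest reply is that 'unexpected' may have been meant loosely, as 'unintended' or 'untoward', in which case foreseen events would be included. The word is undefined, so this cannot be ruled out, and the defect is partly one of definition. The same edit is needed on either reading.

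A second reply is that harm would not go unnoticed. That is right: the events would be managed, participants who stop the intervention are still invited to assessments, and the sources in step 2 above would catch some harm. What stands is narrower: none of it is counted or summarised as a harm outcome.

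A third reply is that distress or a disclosure is not necessarily an effect of the programme. Participants are selected for depressive symptoms, and a disclosure may reveal risk that was already there. This also stands. It is a reason to record events without presuming their cause, and to compare the arms.

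Two stronger readings are tempting, and the documents support neither.

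- A reader might infer from the limits of 20.6% and 10.9% that leaving out foreseen events throws away most of the safety information in a trial this small. The limits would be the same for zero events of any kind, and the number of foreseen events is unknown, so that conclusion does not follow.
- A reader might infer that removing the MFQ risk items contradicts the exclusion for "High levels of current risk". Nothing says that the MFQ supplies that judgement. Eligibility is checked at the first assessment, and how risk is judged there is simply not stated. That is a question of eligibility, separate from the harm outcome.

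**Conclusion.** The concern holds in a limited form. The plan's only harm outcome carries an undefined restricting word. Read in the ordinary way, it excludes three kinds of event that the same document anticipates, and no harms summary is planned. Following the plan as written could therefore yield a report of no adverse effects alongside several foreseeable harms. This goes beyond missing detail, because the stated outcome itself decides which events are reported.

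The size of the effect cannot be derived from the documents. The 56% to 97% chance of at least one event in an arm rests on assumed rates of 5% to 20%, full arms of 16 and independence between participants. The conclusion about wording does not depend on those figures. It rests on the ordinary meaning of 'unexpected' and on there being no other harm outcome in the document. The point concerns what is counted and reported; it implies no change to how any event is managed.

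**What to change.** 1. Delete 'Unexpected'. Define the outcome as all adverse effects, expected or not, from randomisation to the 3-month assessment. Starting at randomisation avoids attributing events at screening or baseline to an arm.
2. Include distress needing action, risk disclosures and stigmatisation already handled under the ethics section. Record them as events, without presuming that the programme caused them. State who records them.
3. Ask the same adverse-effect question in both arms at the existing post and 3-month online assessments. Review the answers under the risk and distress procedures already described. This also reduces reliance on the practitioner, who delivers both interventions and is mainly responsible for gathering the data.
4. Add a harms summary to the analysis section: the number and percentage of participants with each type of event, by arm, with exact 95% confidence intervals and no hypothesis test.
5. Report MFQ worsening separately from events, and only against a reliable-change threshold stated in advance. Without a threshold, a one-point rise would count as harm and ordinary fluctuation would inflate the tally in both arms. The documents give no reliability or standard deviation for the 29-item version, so no value is proposed here.

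The cost is a change of wording, one added question, and a tally of events that are already being managed. The downsides are a higher reported count of adverse effects and a small burden, because someone must review the answers to the added question.
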